3.2 Exclusion Criteria

Clinicians. There are no exclusion criteria for clinicians.

Patients. Visits will be excluded from the primary analysis when they have active cancer. Cancer exclusions (ICD-10 codes) are listed in Appendix A.

3.3 Study Enrollment Procedures

We will seek a waiver of consent for clinician and patient participation. All clinicians treating patients who meet the inclusion criteria in participating practices will be contacted by email to inform them that their patients will be receiving the following assessments: COMM or COMM+PainTracker, depending on clinician study arm assignment.

The COMM is already being delivered as part of standard clinical care. Our study proposes to randomize half of the patients to also receive the PainTracker, which poses no additional risk.

We are requesting a waiver of consent under the Common Rule. The Common Rule (§46.116) specifies that informed consent can be waived when: “(1) The research involves no more than minimal risk to the subjects; (2) The research could not practicably be carried out without the requested waiver or alteration; (3) If the research involves using identifiable private information, the research could not be practicably carried out without the identifiable information; (4) The waiver or alteration will not adversely affect the rights and welfare of the subjects; [and] (5) Whenever appropriate, the subjects will be provided with additional pertinent information after participation.”

Withdrawal of subjects: Patients receive COMM as part of their standard of care at Northwestern Medicine. Patients will not be required to respond to the additional PainTracker surveys, and will continue to receive the same standard of care. After the 9 month intervention, PainTracker surveys will no longer be delivered to patients.

STUDY INTERVENTIONS

3.4 Interventions, Administration, and Duration

The intervention period will be 9-months in length for all participants.

3.5 Handling of Study Interventions

The following study arms will be compared:

Condition 1 (COMM) - On a monthly basis, as part of standard clinical care, patients will receive the Current Opioid Misuse Measure, a 17-item self-report screener to identify and monitor the risk of aberrant opioid-related behavior in chronic pain patients on opioid therapy. The COMM asks patients to report their behaviors over the past 30 days using a five-point Likert-type rating scale. Multiple studies have shown that the COMM can accurately identify patients who are engaging in aberrant opioid-related behavior (defined as medication misuse, abuse, addiction, diversion, and opioid-seeking behaviors) with approximately 80% accuracy. Much of its classification accuracy is because many of the items, while predictive of opioid misuse, do not appear to patients to be asking about opioid misuse.

Condition 2 (COMM+PainTracker) - On a monthly basis, patients will receive both the Current Opioid Misuse Measure (described above) and PainTracker. The latter tracks multiple outcomes relevant to the treatment of chronic pain: pain severity, general activity interference, enjoyment of life interference, sleep (initiating and maintaining), depression, and anxiety. New and returning patients are asked to complete the PainTracker assessment at least one week prior to their appointment.

COMM and PainTracker surveys will be delivered through the patient portal and survey responses will be recorded in the patient electronic health record, and will be visible to the patient's doctor at the time of their next visit. USC will not receive patient survey data, only completion rates.

3.6 Adherence Assessment

In order to ensure that the study interventions are being reliably delivered we will create testing scripts that cover logical and coding variation in EHR-based interventions. Study staff will conduct assessments regularly during the intervention to ensure that tests do not fail.

4. STUDY PROCEDURES

4.1 Schedule of Evaluations

Assessment	Screening: Baseline	Enrollment, Randomization: (Day 1)	Intervention start (Month 1)	Continuously Measured or monitored	Intervention end: (Month 9)	Follow-up period
Clinician-level Assessments						
Demographics		X				
Inclusion/Exclusion Criteria						
Prescribing: Monthly morphine milligram equivalents	X			X		X
Visit-level assessments						
Demographics		X				
Inclusion/Exclusion Criteria		X				
ICD-10 codes	X	X	X	X	X	X

Ordering Data	X	X	X	X	X	X
Pain Tracker/COMM completion rates			X	X	X	
Referral rates to non opioid care			X	X	X	X
Adverse Events			X	X	X	

4.2 Description of Evaluations

4.2.1 Screening Evaluation

Consenting Procedure

We will seek a waiver of consent and HIPAA authorizations for participating physicians and use of patient data for the trial. This approach expedites the implementation phase, maximizes clinician observations and prevents selection bias associated with clinician enrollment.

4.2.2 Enrollment, Baseline, and/or Randomization

Enrollment

This study involves a randomized trial with 286 clinicians to inform the best approaches to patient assessments for opioid at clinical visits. Long-term opioid recipients complete the Current Opioid Misuse Measure as standard clinical practice. PainTracker will appear as part of these required assessments randomly for half the patients of clinicians randomized to the intervention (COMM+PainTracker). If a waiver is granted, enrollment date (RCT implementation date) will be recorded for each clinic.

Assessments

Baseline: At baseline, we will assess clinician baseline prescribing monthly morphine milligram equivalents (MMEs), ICD-10 codes, and ordering data.

Enrollment and Randomization (Day 1). Demographics, inclusion/exclusion criteria, ICD-10 codes, and ordering data.

Intervention start (Month 1). ICD-10 codes, and ordering data, Pain Tracker/COMM completion rates, Referral rates to non-opioid care, adverse events

Continuously measured or monitored. ICD-10 codes, and ordering data, Pain Tracker/COMM completion rates, Clinician

monthly MMEs, Referral rates to non-opioid care, adverse events

Intervention end (Month 9): ICD-10 codes, and ordering data, Pain Tracker/COMM completion rates, Referral rates to non-opioid care, adverse events

Follow-up (Month 10-12): ICD-10 codes, ordering data, Clinician MMEs, Referral rates to non-opioid care.

Randomization

We will use cluster randomization at the physician level to avoid contamination that might occur if individual providers are randomized to multiple interventions. We will carry out block randomization of physicians with respect to historical referral rate (high vs. low) by using a random permutation of physician lists in the statistical computing language R. Patients of clinicians in the first half of the permuted list will receive the PainTracker survey intervention in addition to COMM. The second half will receive the control condition (COMM standard clinical practice). The same intervention (PainTracker survey) will be implemented throughout the 9 month study period. No intervention will occur during the 3 month follow-up period; it will be for outcomes assessment only.

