7. STATISTICAL CONSIDERATIONS

7.1 Sample Size and Randomization

Sample Size: We conduct power on the discrete outcome of the referral. The rate of referrals for mental health and pain treatment is low at Northwestern, but if combined with sleep and physical therapy will be at least 5%. There are 300 clinicians who treat patients at the Northwestern outpatient clinics. There are also 5,159 persons over 65 years of age on long-term opioid therapy within patient registries at Northwestern University's health system with at least one primary care encounter in the past 12 months. Assuming 150 clinicians per condition, each treating 17 patients (i.e., 2,500 patients per condition), $\alpha = 0.05$ for a two-sided

test, an intraclass correlation coefficient of 0.06, and an 80% chance of detecting an effect, requires a 3% difference between groups when the baseline referral rate is 5% and 4% difference between groups when the baseline referral rate is 10% (see **Figure 2**).

Figure 2

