7.4 Data Analyses

For inferential analysis, our *primary hypothesis* is that the proportion of non-opioid referrals will be greater among physicians treating patients who receive PainTracker. We evaluate this with a zero-inflated Poisson model to estimate the number of referrals to non-opioid related care which is then divided by the average number of referrals for each group to estimate the proportion. Our *secondary hypothesis* is that milligram morphine equivalent dose will decrease for persons on high doses of opioid therapy receiving PainTracker. We assume a linear mixed-effects hierarchical knotted spline regression model which offers a flexible way to accommodate non-linear trends before and after the introduction of the intervention.²⁰ This model places a knot at the intervention start date allowing slopes before and during treatment to vary for intervention and control. For our two-group study evaluating this outcome, monthly mean milligram morphine daily dose prescribed for intervention and control, we will place a knot at t^* , the start of the intervention, and evaluate for each comparison between groups:

$$Y = \beta_1 + \beta_2 \text{Time} + \beta_3(\text{Time} - t^*)_+ + \beta_4 \text{Group} + \beta_5 \text{Time} \times \text{Group} + \beta_6(\text{Time} - t^*)_+ \times \text{Group} + \eta + \text{error} \quad [1]$$

where $(z)_+$ is a truncated line function that equals z when z is positive and is equal to zero otherwise, and η is the clinic random effect.

8. **DATA COLLECTION AND QUALITY ASSURANCE**

8.1 **Data Collection Forms**

Data will be collected from electronic medical and billing records and completion rates of PainTracker and COMM surveys.

8.2 **Data Management**

Each of the participating sites will create an extract from their Electronic Medical or Billing Records of the Data Elements. These records will be transferred to the coordinating center as a one time HIPAA compliant limited data set at the end of the study. The CC has created programs and quality control queries for transforming all of the data into a standard model (Observational Medical Outcomes Partnership Common Data Model, version 5.3.1).

The electronic data system, Epic, will have native data capture formats.

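### Clinicians are blocked on historical referral rate, but the primary model as described uses neither the block nor the rate; adding both, in a model that handles clinician clustering, costs almost nothing and gains modest precision

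*Combined protocol and SAP*

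**What the plan says.** Section 4.2.2 makes the physician the unit of randomisation: "We will use cluster randomization at the physician level to avoid contamination". It then adds: "We will carry out block randomization of physicians with respect to historical referral rate (high vs. low". Allocation is 1:1 from permuted lists: "Patients of clinicians in the first half of the permuted list will receive the PainTracker survey intervention in addition to COMM".

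Section 7.4 describes the primary analysis in one sentence, which includes: "We evaluate this with a zero-inflated Poisson model to estimate the number of referrals to non-opioid related care". It names no block term, baseline referral rate, other covariate or clinician-level term. No other section adds one. The secondary model for morphine equivalents, equation [1], has time, group, their interactions and a random effect (η "is the clinic random effect"), again with no block or historical referral term.

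On baseline data, section 4.2.2 says: "At baseline, we will assess clinician baseline prescribing monthly morphine milligram equivalents (MMEs), ICD-10 codes, and ordering data". The schedule in section 4.1 collects ordering data from baseline on, but marks referral rates only from Month 1. The historical referral rate is not defined: neither the referral types, nor the patients, nor the look-back period.

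**The concern.** The analysis should reflect the way the units were randomised. If clinicians are blocked on something that predicts the outcome, the arms are better balanced than under simple randomisation. A model without the block does not credit that balance, so its standard error is too large and the test is conservative.

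A two-level block also uses only part of the information in the underlying rate. The continuous rate can explain further variation between clinicians, and without it that variation stays in the error term.

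The rate has to be known before anyone is randomised, so using it costs almost nothing. If it is not pre-specified, adding it later becomes a post hoc choice on the primary endpoint.

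**Working it through.** **Inputs.** Section 7.1: 150 clinicians per arm, 17 patients each, ICC 0.06, two-sided alpha 0.05, 80% power, detectable difference 3 points at a 5% referral rate and 4 points at 10%. Section 3: 1451 patients and 286 clinicians, so 1451/286 = 5.07 patients each. The documents do not give the correlation between historical and trial-period referral rates, so it is assumed below.

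**1. The plan's own figure.** Design effect = 1 + (17 − 1) × 0.06 = 1.96. Effective n per arm = 150 × 17 / 1.96 = 1301. The difference detectable with 80% power is 2.67 points at 5% and 3.54 points at 10%, which round up to the stated 3 and 4. At exactly 3 and 4 points, power is 87.4% and 88.1%. The figure is reproduced with no allowance for blocking or baseline adjustment.

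**2. The section 3 numbers.** Design effect = 1 + (5.07 − 1) × 0.06 = 1.244. Power for 5% versus 8% is 54.7%.

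**3. How much variance a covariate could remove.** The between-clinician share of the variance of a clinician mean is 0.06 / (0.06 + 0.94/m):
- m = 5.07: 0.245
- m = 17: 0.520

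**4. How well the historical rate measures the clinician.** If true rates are stable and the historical rate rests on h patients, the share of between-clinician variance it explains is 0.06h / (0.94 + 0.06h). With h equal to the trial panel:
- At 5.07 patients: 0.304/1.244 = 0.245. Variance reduction = 0.245 × 0.245 = 0.060. Equivalent clinicians = 286/(1 − 0.060) = 304, or 18 more.
- At 5.07 patients, with true rates correlated 0.8 between periods: 0.060 × 0.64 = 0.038; 286/(1 − 0.038) = 297, or 11 more.
- At 17 patients: 0.520 × 0.520 = 0.27.

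These reductions are measured against an analysis that ignores blocking, which has already removed part of this variance by design.

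**5. Linear simulation on clinician-level rates** (3000 runs; beta-binomial clinician rates, ICC 0.06; historical rate from an independent earlier period of equal size with stable true rates; median split; 1:1 within block; 5% baseline). Analysing one rate per clinician takes care of clustering.

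| Setting | Quantity | Unadjusted | Block | Block + rate |
|---|---|---|---|---|
| 150 × 17, null | True SD of estimate | 0.00798 | 0.00798 | 0.00724 |
| 150 × 17, null | Mean standard error | 0.00853 | 0.00798 | 0.00728 |
| 150 × 17, null | Rejection | 3.5% | 5.2% | 5.1% |
| 150 × 17, +2 points | Power | 60.0% | 64.5% | 72.8% |
| 143 × 5, +3 points | Power | 56.1% | 56.4% | 58.6% |

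The block leaves the true SD unchanged and corrects the standard error. The continuous rate lowers the true SD. At 150 × 17 the variance falls by 1 − (0.00724/0.00798)² = 18% beyond blocking. Measured by standard errors from the unadjusted analysis, it falls by 1 − (0.00728/0.00853)² = 27%, in line with step 4.

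**6. The named model without a clinician term** (zero-inflated Poisson with exposure offset, 300 runs). At 150 × 17 it rejected about 8–9% of the time under the null, with or without the covariates (5% baseline: 9.0%, 9.0% and 8.7%), because its standard error was too small (unadjusted 0.145 against a true SD of 0.170). At 143 × 5 with 5% baseline, rejection was 5.3%, 6.0% and 5.3%, so no clear inflation showed there. The Monte Carlo error of a 5% rate on 300 runs is about 1.3 points.

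**The case against.** Three objections carry weight.

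First, the gain is small where it is most wanted. At about 5 patients per clinician, the block adds 0.3 power points and the block with the rate adds 2.5. A reader might infer that the covariates would bring the trial back to its stated power. They would not: power for 5% versus 8% stays below 60%. A reader might also assume that the historical rate explains 30–50% of between-clinician variance, which would give 0.245 × 0.3 to 0.245 × 0.5, a 7–12% reduction worth 22–40 clinicians. Even with fully stable rates, that needs a history of about 7 to 16 patients per clinician (0.3 × 0.94/(0.06 × 0.7) = 6.7; 0.94/0.06 = 15.7). The documents describe no such panel or window.

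Second, the claim that the standard error is too large assumes that clustering has been handled. For the bare model in section 7.4, step 6 found the opposite at 17 patients per clinician. Covariates alone would then sharpen a standard error that is already too small. This stands, and it changes the fix.

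Third, the plan is silent on adjustment; it does not rule it out. It also does not say that the historical rate is the same composite as the primary outcome, so treating it as the outcome's baseline value is an inference. Baseline ordering data are already scheduled, so the source records may be in hand. All true. But a primary analysis should state its covariates, and the derived variable is undefined.

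Nor does the omission bias the comparison: blocking balances the arms whether or not the model includes it.

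**Conclusion.** The point holds as an inexpensive improvement, not as an error that threatens the result. As described, the primary model does not reflect the blocked randomisation. With clustering handled, omitting the block makes the test conservative, and omitting the continuous rate loses some real precision.

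On the section 3 numbers the variance saving is at most about 6%, if clinician rates are stable and the historical panel is of similar size; it is about 4% if true rates correlate 0.8 between periods. At the 17 patients per clinician of section 7.1 the gain is worth having: 60% to 73% power for a 2-point difference.

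The direction is well supported. The size rests on an unstated correlation, on a linear simulation standing in for a log-link count model, and on permutation being carried out within each block. The sample-size mismatch and the missing clinician-level term are larger problems, and this change solves neither by itself.

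**What to change.** In section 7.4, pre-specify two fixed covariates in the count part of the primary model: the randomisation block (high/low) and the clinician's historical referral rate as a continuous term. Put them in a model that also accounts for clustering by clinician, through either a clinician random effect or clinician-clustered robust standard errors. The covariates should not go in without that.

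In section 4.2.2, define the historical rate as the three-component composite (mental health, physical therapy, sleep medicine) over a fixed window before randomisation, for example 12 months. State which patients count towards it and the cut between high and low. Add the rate to the baseline column of the schedule in section 4.1.

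The cost is a sentence or two in section 7.4, a definition in section 4.2.2 and one schedule entry. A historical rate is already needed to form the blocks, and baseline ordering data are already collected. The change should be made before outcome data are seen.

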5. SAFETY ASSESSMENTS

For patients who were noted to have opioid prescriptions abruptly stopped, emergency room visits or hospitalizations with a diagnosis that could represent a serious complication of untreated pain will be extracted from study site EHRs and reported to the Data and Safety Monitoring Board. Relative rate of ED visits between study conditions will also be evaluated.

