5.1 Specification of Safety Parameters

Data elements from qualifying visits for providers enrolled in the study will be collected from the electronic health record. Aggregate counts of total visits across sites for which the intervention was implemented, for high dose opioid patients, if abrupt changes to dose (> 20% morphine equivalent daily dose) were made. Such cases will be examined closely to determine if unsafe drops in opioids occurred.

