5.2 Methods and Timing for Assessing, Recording, and Analyzing Safety Parameters

The Roybal Standing Data and Safety Monitoring Board will be providing oversight for this study, and has determined the cadence of our reporting (6 and 12 months). The data analyst at Northwestern University will pull the required patient data for analysis from the NU electronic health records one month prior to the 6 and 12 month report due dates. The PIs and Co-Is will review in our team

meeting before delivering to the Data and Safety Monitoring Board. When necessary, our NU Site PI ([name]) will conduct chart reviews to investigate any safety concerns.

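### No adverse-event collection is scheduled in months 10-12, and no all-patient comparison by arm is stated for hospitalizations, abrupt discontinuations or dose changes

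*Combined protocol and SAP*

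**What the plan says.** Four parts of the combined protocol and SAP bear on this point.

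- **Schedule.** In section 4.1 the row "Adverse Events" is marked at intervention start, under continuous monitoring and at intervention end. The follow-up cell is blank. Section 4.2.2 agrees. Its month 9 entry reads "Intervention end (Month 9): ICD-10 codes, and ordering data, Pain Tracker/COMM completion rates, Referral rates to non-opioid care, adverse events", while the next entry reads "Follow-up (Month 10-12): ICD-10 codes, ordering data, Clinician MMEs, Referral rates to non-opioid care". The same section says of those months: "No intervention will occur during the 3 month follow-up period; it will be for outcomes assessment only".
- **Extraction of serious events.** Section 5 begins "For patients who were noted to have opioid prescriptions abruptly stopped, emergency room visits or hospitalizations" and goes on to require a diagnosis that could reflect a serious complication of untreated pain. These events go to the safety board. The section then adds: "Relative rate of ED visits between study conditions will also be evaluated".
- **Dose changes and definitions.** Section 5.1 describes "Aggregate counts of total visits across sites for which the intervention was implemented", for high-dose patients with abrupt changes above 20%. Section 5.3 defines an adverse event as abrupt discontinuation when the latest prescription was above 49 morphine equivalent daily dose, or an event reported to staff. It also says that ED visits and prescribing increases above 20% will be evaluated.
- **Timing of safety data.** Section 5.2 has the analyst pull data "one month prior to the 6 and 12 month report due dates".

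**The concern.** There are two separate issues.

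The first is coverage over time. PainTracker stops after month 9. If opioids are stopped late in the intervention, or after the surveys end, the complications fall in months for which no adverse-event collection is scheduled. Orders and diagnoses are still being gathered in those months.

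The second is the population. Being abruptly stopped happens after randomization, and the protocol itself expects the arms to differ in opioid decisions. Section 7.4 hypothesizes lower doses among high-dose patients receiving PainTracker, and section 2.1 says that a focus on misuse alone encourages forced tapering. If stopping differs by arm, in either direction, the stopped patients in the two arms are not comparable groups. Counts drawn only from them then describe stopping as much as they describe harm.

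Consent is waived for patients and clinicians (section 3.3), and the board's recommendations rest on these safety reports (sections 6 and 7.2). The board should therefore be able to see harms by randomized arm over everyone eligible.

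**Working it through.** The plan gives no safety rate or count to reproduce. The check is a reading of the passages plus an illustration with assumed rates.

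**1. Coverage in time.** Scheduled adverse-event collection runs over months 1 to 9 of 12. The uncovered share is 3/12 = 25% of calendar time, the same in both arms. It is not a share of events.

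**2. Safety pulls.** Counting the reports from intervention start (an assumption, since section 5.2 does not give the origin), the pulls fall at 6 − 1 = month 5 and 12 − 1 = month 11. The second covers the whole intervention period and at most 2 of the 3 follow-up months. It lies inside the window where sections 4.1 and 4.2.2 list no adverse events, and it cannot reach the end of month 12.

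**3. What is compared by arm, on the stated text.**

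| Harm | Population stated | Between-arm comparison stated |
|---|---|---|
| ED visits, any | not given | yes (section 5), with no window, model or clustering |
| ED visits with a serious diagnosis | abruptly stopped patients | no |
| Hospitalizations with a serious diagnosis | abruptly stopped patients | no |
| Abrupt discontinuations | latest prescription above 49 (section 5.3) | no |
| Dose changes above 20% | high-dose patients, arm unclear (section 5.1); increases also in section 5.3 | no |

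The analysis plan in section 7.4 contains no safety analysis.

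**4. What the restriction could do.** Let s be the risk of an abrupt stop, e the serious-event risk if stopped, and u the risk if not stopped.

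- Extracted events per randomized patient: s × e
- All events per randomized patient: s × e + (1 − s) × u
- Share extracted: s × e / [s × e + (1 − s) × u]

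Assumptions: e = 10% in both arms, u = 2% or 5% in both arms, control s = 5%, and intervention s = 2.5%, 5% or 10%.

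Control arm, u = 2%: 0.05 × 0.10 = 0.005, and 0.005 + 0.95 × 0.02 = 0.024, so 0.005/0.024 = 21% of serious events are extracted. With u = 5%: 0.005/(0.005 + 0.0475) = 10%.

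Intervention arm, s = 10%, u = 2%: 0.010 + 0.90 × 0.02 = 0.028. The all-patient ratio is 0.028/0.024 = 1.17 and the extracted ratio is 0.010/0.005 = 2.0. The other cases follow in the same way:

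| Intervention s | Ratio among stopped | Ratio of extracted events per randomized patient | All-patient ratio (u = 2%; 5%) | Share extracted, intervention (u = 2%; 5%) |
|---|---|---|---|---|
| 2.5% | 1.0 | 0.5 | 0.92; 0.98 | 11%; 5% |
| 5% | 1.0 | 1.0 | 1.00; 1.00 | 21%; 10% |
| 10% | 1.0 | 2.0 | 1.17; 1.05 | 36%; 18% |

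Taking the 1,451 patients of section 3 as about 725 per arm (equal split assumed), the extracted events would number about 725 × 0.005 = 3.6 in control, against 1.8, 3.6 or 7.3 under the intervention. The ratios and shares do not depend on that sample size.

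When stopping differs, neither the ratio among stopped patients nor the ratio of extracted events matches the all-patient ratio. When stopping is equal and the other risks are equal, every ratio is 1.0.

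**The case against.** A reader might infer that harm cannot be compared fairly between the arms at all. The documents do not support that. Section 5 plans a relative ED-visit rate between conditions and does not confine it to stopped patients, and section 5.3 brings in ED visits and dose increases. Nor does any section plan a comparison limited to stopped patients. With board reporting and chart review (section 5.2), the restricted extraction reads as case surveillance, which is a proper use. Abrupt discontinuation above the section 5.3 threshold is itself an adverse event in months 1 to 9, so a rise in such stops would be captured there. What stands against this is that no reporting of those stops by arm is stated.

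A reader might also infer that late events are never recorded. That goes too far. Section 5 sets no time limit on the ED and hospital extraction, the second pull appears to reach about month 11, and orders through month 12 could show discontinuations. The gap is equal in both arms, so it loses late events and does not bias the comparison by itself.

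Third, section 5.1 might be taken to count the intervention arm only. It speaks of sites, randomization is by physician, and its opening sentence covers all enrolled providers. The wording is unclear, but it does not establish a one-arm count.

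Finally, section 5.4 points to a separate Data and Safety Monitoring Plan that is not among the documents. Tables by arm may be specified there. If so, part of this point is met by a cross-reference.

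**Conclusion.** The point holds as a gap in specification that is cheap to close. It does not show that the safety comparison is invalid.

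Two things are established by the text. Adverse events are absent from both follow-up entries, 25% of the observation time, and the sections on schedule and safety pulls do not fit together. Serious-diagnosis ED visits and hospitalizations are extracted only in a subset formed after randomization, with no all-patient comparison by arm stated for hospitalizations, abrupt discontinuations or dose changes above 20%.

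The size of any distortion is not known. In the illustration, the restricted extraction picks up 5% to 36% of serious events, and its ratio per randomized patient is 0.5 or 2.0 where the all-patient ratio lies between 0.92 and 1.17. Those figures rest entirely on assumed rates and on the intervention changing abrupt stopping. That change is plausible given the protocol's own hypothesis, but it is not shown. The month 11 timing rests on counting from intervention start.

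**What to change.** 1. Add adverse events to the follow-up entries in sections 4.1 and 4.2.2, and reconcile these with sections 5 and 5.2. State the origin from which the 6 and 12 months are counted, and time the final data pull so that it covers month 12.
2. Extract ED visits and hospitalizations for all eligible patients in both arms.
3. Report these, together with abrupt discontinuations and dose changes above 20%, by randomized arm. Use all eligible patients as denominator and account for clustering by clinician. State the window and model for the ED-visit comparison already planned.
4. Reword section 5.1 so that it is plain that both arms are counted.
5. Keep the extraction in abruptly stopped patients, labelled as case review.
6. If the Data and Safety Monitoring Plan already contains any of this, cite it in section 5.

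The cost is a wider query in EHR pulls that are already scheduled, a later final pull, and slightly longer board tables. No clinical rule changes.
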